This study will enroll ambulatory community-dwelling men and women age ≥ 65 years. Participants must have a habitual dietary intake of protein of ≤ 0.8 g/kg/d and not be vegetarian. Participants must not change their habitual diet, habitual exercise regimen, or not enter into a weight loss program during the 24-wk study. Participants will be underactive based on a screening questionnaire, the validated Rapid Assessment of Physical Activity (RAPA).⁶² Participants must have an estimated GFR ≥ 50 ml/min/1.73 m². Participants who are taking a daily calcium supplement (as carbonate, acetate, citrate) can participate in the trial as long as they are willing to switch to a calcium triphosphate supplement provided to them by the study.

Exclusion criteria:

Daily protein intake >0.8 g/kg/day and highly fit older adults (based on RAPA) will be excluded from the study. Drug and medical exclusions are imposed to maximize participant safety. Apart from safety considerations, there are medications known to have a large effect on our muscle outcomes (e.g., glucocorticoids, hormones) and that are likely to dilute the effect of whey protein and KHCO₃ supplementation on our outcomes. However, we expect to have only small numbers of users of any specific medication so it is unlikely that we will be able to explore each of these. Therefore, we plan to exclude users of these medications.

Medications and supplements

1. oral glucocorticoid use for > 10 days in the last 3 months
2. anabolic and gonadal hormones in the last 6 months
3. Tamoxifen/raloxifene in the last 6 months
4. regular use of alkali-producing antacids (> 3 times per week)
5. potassium containing supplements or products (i.e., KCl or salt substitutes)
6. NSAIDS >3 times per week
7. antacids containing calcium carbonate, aluminum hydroxide, magnesium hydroxide, or calcium acetate
8. insulin
9. sulfonylureas
10. SGLT2 inhibitors

Conditions/Diseases

1. a lower extremity fracture in the last year
2. kidney stones in the past 5 years
3. creatinine clearance < 50 ml/min (assessed from serum creatinine with use of the Modification of Diet in Renal Disease (MDRD) Study equation).⁶³
4. hyperkalemia (serum potassium >5.3 mEq/L; normal range 3.5-5.3 mEq/L)
5. elevated serum bicarbonate (>33 mmol/L; normal range 21-33 mmol/L)
6. serum calcium outside the range of 8.3-10.2 mg/dl
7. uncontrolled diabetes mellitus defined as having fasting blood >150 or hemoglobin A1c $>8\%$
8. untreated thyroid or parathyroid disease

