Steps to encourage retention include: a welcoming and cordial environment on each study visit and recipes that contain information about how to incorporate the powder packets into each meal throughout the study. **All participants** will be counseled by our dietary team at the start of the study and throughout the study (weeks 6, 12, 18) to promote adherence to their usual protein intake and to the powder packets. For study pills, participants will record compliance in diaries and return these diaries at each visit. Nursing staff will also perform pill counts. Diaries will also be kept for the powder packets. Participants will contact our research coordinator if they have concerns about the powder packets or other concerns (scheduling, etc). More objective adherence measures for the whey protein intervention will be recorded in 24h UNi measurements, and for the KHCO₃ intervention will be recorded in 24h net acid excretion (NAE) measurements.

STUDY DESIGN

This study is a 2x2 factorial design single center double-blind randomized controlled clinical trial. Study duration is 24 weeks. See study timeline chart and study procedures chart below.

Study Timelines

	Year 1	Year 2	Year 3	Year 4	Year 5
Preparation of study powder packets and pills	■				
Preparation of recruitment materials	■				
Subject recruitment/screening/randomization	■	■	■	■	
Enrollment/intra-study visits	■	■	■	■	■
Muscle strength and performance testing		■	■	■	
Bioassays		■	■	■	
Quality control complete/Data files locked					■
Data analyses and interpretation					■
Manuscript preparation and submission					■

	Pre-screen	Screen	Enroll Day -3	Baseline Day 0	1 wk Day 7	3 wk Day 21	6 wk Day 42	9 wk Day 63	12 wk Day 84	15 wk Day 105	18 wk Day 126	21 wk Day 147	Final 1 Day 164	Final 2 Day 168
Study Visit		1	2	3	3a		4		5		6		7	8
Consent		X	X											
Medical history		X	X											X
Height		X												
Weight		X		X			X		X		X			X
Blood pressure		X		X					X					X
EKG		X												
Protein intake assessment ^a	X													
Physical activity assessment ^b	X			X										X
Whole body DXA scan				X										X
D ₃ -Creatine Dilution ^c			X	X	X								X	X
Double leg press				X					X					X
Knee extension				X					X					X
Handgrip				X										X
Modified SPPB				X										X
Diet assess (recall) ^d				X			X		X		X			X
Diet counseling ^e	X		X			X		X		X				
Phone call (Adherence/ Tolerance)					X			X		X		X		
Screening blood ^f		X												
Study blood ^g				X	X		X							X

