^h Return 24-hr urine

- Baseline visit and Final 2 visits: Ni, NAE, Cr
- Five 5-ml aliquots will be archived at the Baseline and Final 2 visits.

ⁱ Capsules of KHCO_3 /placebo and Ca/D supplements dispensed. Participants will take 1 capsule after each meal for 14 days (to adapt to the KHCO_3) and then increase to 2 after each meal (6/d total) thereafter.

^j Protein packets will be dispensed by the dietary team. Subjects will take the whey protein supplement with each meal except on the days 164 and 168 (Final Days 1 and 2) when they will skip the packet with their evening meal. The goal of the packets is to bring total intake of protein to 1.5 g/kg/d (or 15-25 g of additional protein with each meal depending on body weight).

^k Adherence to study pills will be assessed by capsule counts and by capsule diaries. Adherence to the protein packets will be assessed by packet counts and diaries. Objective measures of adherence are NAE and UNi.

Medical history questionnaire

The medical history includes medication and supplement use, general medical history, and past and current cigarette smoking and alcohol use. The questionnaire will be conducted in person or by telephone if preferred by the study participant.

Study interventions

Whey protein powder. Protein packets will contain 15-25g of whey protein each. We will advance all participants to

Weight category	A (< 70 kg)	B (70 – 90 kg)	C (91+ kg)
Dosing group	15g per meal	20g per meal	25g per meal

approximately 1.5 g/kg/d based on their body weight and typical baseline protein intake. The whey protein and its isocaloric placebo (maltodextrin - an easily digestible flavorless starch) powder will be flavorless and purchased in bulk at <http://www.bulkfoods.com>. The dietary team will make the packets and distribute to participants at baseline and weeks 6, 12, and 18. The packets will be mixed with water and the dietary team also will provide a menu for how to incorporate the powder into recipes. The whey and placebo powder packets will be isocaloric.

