In a modified ITT analysis set, we will exclude from the ITT sample those participants who –took less than 10% of whey protein isolate or KHCO₃ and those with any major protocol deviation.

In a per protocol analysis set, we will further restrict the mITT sample to participants who took whey protein isolate and KHCO₃ throughout the 24 weeks with an average compliance of at least 75%.

6. Trial Population

a. Eligibility

The inclusion criteria are:

- ambulatory community-dwelling men and women age ≥ 65 years
- habitual dietary intake of protein of ≤ 0.8 g/kg/d and not be vegetarian

- willing not to change their habitual diet, habitual exercise regimen, or enter into a weight loss program during the 24-wk study
- underactive based on the validated Rapid Assessment of Physical Activity (RAPA)
- estimated GFR $\geq 50 \text{ ml/min}/1.73 \text{ m}^2$

Participants who are taking a daily calcium supplement (as carbonate, acetate, citrate) can participate in the trial if they are willing to switch to a calcium triphosphate supplement provided to them by the study.

The exclusion criteria are

- users of the following medications or supplements:
 1. oral glucocorticoid use for > 10 days in the last 3 months
 2. anabolic and gonadal hormones in the last 6 months
 3. Tamoxifen/raloxifene in the last 6 months
 4. regular use of alkali-producing antacids (> 3 times per week)
 5. potassium containing supplements or products (i.e., KCl or salt substitutes)
 6. NSAIDS >3 times per week
 7. antacids containing calcium carbonate, aluminum hydroxide, magnesium hydroxide, or calcium acetate
 8. insulin
 9. sulfonylureas
 10. SGLT2 inhibitors
- individuals with the following conditions/diseases:
 1. a lower extremity fracture in the last year
 2. kidney stones in the past 5 years
 3. creatinine clearance $< 50 \text{ ml/min}$ (MDRD equation)
 4. hyperkalemia (serum potassium $>5.3 \text{ mEq/L}$; normal range 3.5-5.3 mEq/L)
 5. elevated serum bicarbonate ($>33 \text{ mmol/L}$; normal range 21-33 mmol/L)
 6. serum calcium outside the range of 8.3-10.2 mg/dl
 7. uncontrolled diabetes mellitus (fasting blood >150 or hemoglobin A1c $>8\%$)
 8. untreated thyroid or parathyroid disease
 9. significant immune disorder
 10. current unstable heart disease
 11. Crohn's disease
 12. active malignancy or cancer therapy in the last year
 13. alcohol use exceeding 2 drinks/day
 14. current peptic ulcers or esophageal stricture
 15. milk protein allergy

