Difference in estimated least square mean slopes, the corresponding 95% CI, and p-value will be reported. We will use the p value from the type III F-test of the fixed effect parameter for the intervention group by time interaction. Denominator degrees of freedom will be estimated using the Kenward-Roger approximation with an unstructured covariance matrix and the between-within method otherwise.

- We also will present results for outcome measures at follow-up within each of the four factorial groups in the 2×2 design. We will test for interaction by extending the multivariable linear models described above by simply adding the appropriate interaction terms. However, we anticipate insufficient precision on the interaction estimates to rule out interaction.
- We will repeat analyses in the mITT and per protocol samples.

c. Subgroup Analyses

We will perform subgroup analyses by sex, NAE (<15 mmol/day vs. ≥ 15 mmol/day), protein intake based on average 3-day food recall (≤ 0.8 gm/kg/day vs. > 0.8 gm/kg/day), no sarcopenia vs. sarcopenia (defined as maximum grip strength <35.5 kg (men) and <20 kg (women) in either hand and/or gait speed <0.8 m/sec.

d. Missing data

Descriptive tables of baseline characteristics stratified by arm will include the frequency and percentage of missing values. In attrition analyses, we will then compare these variables between subjects who drop out and subjects with complete outcome data. The number of missing primary outcome data points at each time point, by intervention arm, will be reported in the CONSORT participant flow diagram.

For the primary analyses, we will analyze all available follow-up outcome data using restricted maximum likelihood estimation, under the assumption that data are missing at random.

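### No stop date is set for alkaline calcium supplements before the baseline 24-h urine, so baseline NAE may carry outside alkali into the NAE subgroup and into NAE change as an adherence reading

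*Protocol*

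**What the plan says.** **Eligibility.** Under the protocol's Inclusion criteria, daily users of alkaline calcium salts are eligible "as long as they are willing to switch to a calcium triphosphate supplement provided to them by the study". SAP 6a repeats the rule: "if they are willing to switch to a calcium triphosphate supplement provided to them by the study". Both ask only for willingness. Neither gives a date for the switch or a minimum time off the old salt.

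**Dispensing.** Footnote i of the study procedures chart, attached to the study capsules row, has the study capsules "and Ca/D supplements dispensed". The first mark in that row is Baseline, Day 0.

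**Urine.** Footnote h lists the 24-h urine measurements as "Baseline visit and Final 2 visits: Ni, NAE, Cr". Footnote d puts the three baseline diet recalls between Enrollment (Day -3) and Baseline, with the urine collected on the third recall day. The dietary recall section asks for days typical of the participant's usual diet and says nothing about supplements.

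**Use of NAE.** SAP 7c plans a subgroup analysis by "NAE (<15 mmol/day vs. ≥ 15 mmol/day") without naming the visit. The protocol's Retention section says that objective adherence "for the KHCO₃ intervention will be recorded in 24h net acid excretion (NAE) measurements". SAP 5b also names NAE as an objective adherence measure, and gives no rule for turning it into an adherence judgement.

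**The concern.** The plan treats outside alkali as something to keep out. The medication exclusions cover regular use of alkali-producing antacids and antacids containing calcium carbonate or calcium acetate. The switch to calcium triphosphate serves the same purpose, but as scheduled it comes after the one pre-treatment NAE measurement. NAE is measured only at Baseline and Final 2, so no later pre-treatment value can replace a contaminated one.

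Two uses of NAE are exposed:

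- **Subgroup.** The SAP's rationale is that net acid load helps decide whether the diet builds or breaks down muscle, so the NAE subgroup bears on the trial's premise. A participant whose baseline NAE is low because of a supplement that is then withdrawn carries a label that does not describe the acid load during treatment. Randomisation does not correct that label.
- **Adherence read as change from baseline.** For a switcher on KHCO₃, loss of the calcium alkali offsets part of the expected fall in NAE. For a switcher on placebo capsules, NAE rises with no change in behaviour.

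**Working it through.** The plan states no figure on this point, so there is none to reproduce. The check is the order of events, followed by a range under stated assumptions.

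**Order of events**

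| Step | When | Source |
|---|---|---|
| Supplement use recorded | Screening | Protocol, Telephone Prescreening |
| Baseline 24-h urine collected | Third recall day, between Day -3 and Day 0 | Chart, footnote d |
| Urine returned | Day 0 | Chart, 24-h urine row |
| Study calcium first dispensed | Day 0 | Chart, footnote i |
| Old calcium salt stopped | Not stated | – |

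This takes the calcium in footnote i to be the calcium triphosphate of the eligibility rule; no other dispensing is described. A participant who changes products when the replacement is handed over has therefore collected the baseline urine on the old salt.

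**Shift in one user's NAE (assumed inputs)**

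Base supplied (mEq/d) = 2 × mg calcium / 40.08:

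- 500 mg: 25.0
- 1000 mg: 49.9
- 1200 mg: 59.9

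NAE shift = base supplied × fraction absorbed as net alkali. With 20% to 40%:

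- low: 25.0 × 0.2 = 5.0 mEq/d
- high: 59.9 × 0.4 = 24.0 mEq/d

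For scale:

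- Against the 15 mmol/day cut: 5/15 = 0.3 to 24/15 = 1.6 times the cut-point.
- Against the study dose of 6 × 13.5 = 81 mmol/d: 5/81 = 6% to 24/81 = 30%.
- Illustration: 1000 mg/d at 30% shifts NAE by 49.9 × 0.3 = 15.0, which takes a participant from 29 to 14.

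**Participants moved below the cut (wider assumed inputs)**

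The documents give no share of users, no dose and no NAE distribution. Assume 500 to 1000 mg/d with 10% to 50% reaching the urine (shift 2.5 to 25), normal NAE off alkali with mean 15 to 45 and SD 15 to 25 mmol/d, and 5% to 30% users among 120 participants.

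Share of users mislabelled = P(15 ≤ NAE off alkali < 15 + shift).

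| Case | Mean, SD | Shift | Share of users | User share | Participants of 120 |
|---|---|---|---|---|---|
| Low | 45, 15 | 2.5 | 0.011 | 5% | 120 × 0.05 × 0.011 = 0.1 |
| Middle | 30, 25 | 10 | 0.146 | 10% | 120 × 0.10 × 0.146 = 1.8 |
| High | 30, 15 | 25 | 0.589 | 30% | 120 × 0.30 × 0.589 = 21.2 |

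**Change from baseline**

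A user's NAE change is pushed upward by that user's shift. Averaged over an arm, this is 0.05 × 2.5 = 0.1 to 0.30 × 25 = 7.5 mmol/d. Randomisation makes it equal in expectation with and without KHCO₃.

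**The case against.** **The documents do not say that the old salt continued until Day 0.** Supplement use is asked about at Screening, medical history is taken again at Enrollment, and staff could have told users to stop at either visit. The protocol also refers to a Manual of Operating Procedures that is not among these documents. This stands. A reader might infer that baseline NAE was in fact measured on alkali and that the subgroup is misclassified. The texts support only that this may have happened, because the one scheduled handover comes after the urine and no stop date is written.

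**A baseline taken on habitual intake is a legitimate effect modifier.** This stands in part. It would hold if the habit continued, but these participants give up the salt on entering the trial, so the reading does not describe their acid load under treatment.

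**SAP 7c does not say which visit defines the subgroup.** True. Baseline is the natural reading because KHCO₃ alters the final value, but it remains an assumption.

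**The adherence consequence is small.** This largely stands. No rule converts NAE into an adherence call. SAP 5c defines the modified ITT set by the amount taken and major deviations, and the per-protocol set by average compliance of at least 75%. A reader might also infer bias in the KHCO₃ comparison. The documents do not support that: the final urine follows 24 weeks of study supplements, randomisation balances switchers in expectation, and the primary ANCOVA does not use NAE.

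**The size is entirely assumed.** True. Nor is the label exact without this problem: it rests on a single 24-h collection, with laboratory precision for NAE given as 10.1%.

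**Conclusion.** The gap holds, as a minor point. As written, the eligibility rule, the dispensing footnote and the urine schedule place the calcium switch after the only pre-treatment NAE measurement. Baseline NAE may therefore reflect outside alkali in an unknown number of participants.

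The possible harm is confined to two places: labels in the NAE subgroup, if baseline NAE defines it, and NAE change as an individual adherence reading, if it is used that way. The final NAE level, the randomised contrast, the primary ANCOVA, and the modified ITT and per-protocol sets are untouched.

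The assumed shift of about 5 to 24 mEq/d in users is large beside a cut-point of 15, but the number of participants concerned could be close to none. The wide range of 0 to 21 shows mainly that the documents do not settle it. The conclusion assumes that some users did not stop before the urine and that calcium triphosphate does not supply comparable alkali.

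**What to change.** Reconcile the eligibility rule, footnote i and the baseline urine schedule so that the switch precedes the collection, and state when switching actually took place. The documents give no basis for a particular interval, so that is for the sponsor to set.

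The SAP of May 2024 describes randomisation in the past tense, so enrolment appears complete and the working remedy is an addition to the SAP:

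1. State in 7c that baseline NAE defines the subgroup.
2. Flag prior users of calcium carbonate, acetate or citrate from the supplement-use data already collected, provided the product was recorded.
3. Repeat the NAE subgroup analysis without them.
4. State in 5b whether NAE is read as a final level or as change from baseline; if change is used, repeat that summary without them too.

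This should be fixed before outcome data are examined by group, in keeping with SAP section 1, so that the exclusion is not post hoc. The cost is one extra sensitivity analysis and a slightly smaller subgroup sample, with no new visits or assays.

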Return 24h urine ^h				X										X
Study capsules ⁱ				X			X		X		X			X
Study powder packet ^j				X			X		X		X			X
Adherence ^k							X		X		X			X

^a Two-item protein intake questionnaire on telephone prescreening.

^b To recruit participants who are underactive at baseline, we will use the RAPA, a validated 9-item questionnaire at prescreening and recruit those with scores <5. Intrastudy, changes in physical activity could modify the anticipated responses to treatment. Therefore, we will assess leisure, household, and occupational activity in the past 40 days with use of the Physical Activity Scale for the Elderly (PASE) questionnaire with 10 items and a score ranging from 0 to 400 with higher scores reflecting greater levels of activity at Baseline and Final Day 2.⁶⁴

^c A stable deuterium (D₃)-labelled creatine capsule (60 mg) will be administered to participants at the Enrollment and Final Day 1 visits. A second void of fasting morning urine will be collected on the Baseline and Final Day 1 and 2 visits for analysis of creatine to creatinine. In a subset of participants coming in for a Week 1 safety lab, we will also request a second void of fasting morning urine for analysis of creatine to creatinine on the supplements early in the course of the study. This is to measure the creatine component coming from the diet load.

^d Three consecutive 24-hr dietary recalls will be done for 3 days at the beginning of the study (between the Enrollment and Baseline visits). The third recall day will coincide with the 24-hr urine collected. We will also collect 24-hr recalls on weeks 6, 12, 18, and Final Day 2 to track their diet during the study.

^e Our research dietitian will counsel participants on how to mix the powder packets in water at Baseline and provide a variety of flavors. On weeks 6, 12, and 18, the dietitian will be providing counseling to maintain protein intake in self-selected diets intra-study.

^f Screening blood for routine fasting blood chemistries including serum creatinine (Cr), potassium (K), HCO₃⁻.

^g Fasting study blood:

- Baseline: serum 25-hydroxyvitamin D (25OHD), IGF-1, HCO_3^-
- If the participant is on an ARB, ACEI or potassium-sparing diuretic, a 1 week safety blood for serum K will be drawn. A 6 week safety blood draw to check serum K and Cr (for GFR estimation) will be drawn in all participants.
- At Final Day 2: IGF-1, HCO_3^-
- Ten 0.5 ml aliquots of serum will be archived on the Baseline visit and Final 2-wk visit.

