3-day dietary records-assisted recall – Three consecutive 24hr dietary recalls will be done for 3 days at the beginning of the study. The third recall day will coincide with the 24-hr urines collected for NAE, Ni, and Cr. Both the recalls and urine collections will be done on “normal days” so as to be most representative of the participant’s normal diet pattern. Having 24-hr recalls on the day of the 24-hr urine collections will enable us to link specific foods to daily dietary protein intake and NAE. This diet information will also enable us to adjust our 24-hr UNI measurements for nitrogen intake, and thereby refine the assessment of UNi as a surrogate for protein intake and muscle catabolism at end of study following unblinding. Recalls will also be conducted on weeks 6, 12, 18 and Final Day 2 to track protein intake and NAE throughout the study. 24-hr recalls were used in NHANES, and this will allow us to compare intakes of our participants to national averages. Subjects will be given detailed instructions and measuring aids (a measuring cup, spoons, a ruler and a Food Amounts Booklet) and asked to record everything they eat and drink. They will report what they have consumed to a trained diet technician each day. The 1st recall will highlight what level of food intake detail will be needed to report for the remaining recall days. The dietary interview training is adapted from the 24-hr recall protocol used by the Nutrition Coordinating Center, Minn, MN, <http://www.ncc.umn.edu/index.html>. It is recognized that having to write food items down may alter what participants choose to eat; however, this approach with frequent contact and coaching is likely to give more accurate intake information in our study population than the feasible alternatives, including diet records which do not involve daily staff interaction. The food lists will be coded and analyzed with use of the Minnesota database (NDSR software version 2018, developed by the Nutrition Coordinating Center, U. of Minn., Minn, MN). From this we will attain specific information on food group and nutrient intake, as well as protein nitrogen intake.

Dual energy x-ray absorptiometry (DXA) scans for lean tissue mass

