Lean tissue mass will be measured on total body DXA scans with a precision in our laboratory of 0.67%.⁶⁵ It will be measured on a Hologic Horizon-A (Bedford, MA). The scanner utilizes IRIS Enterprise-APEX for systems on APEX 4.xx which includes DICOM Storage, DICOM Modality Worklist, Remote Physician's Viewer Physician's Report, Writer HL7 Enterprise Data Management Installation. Participants will be scanned wearing light clothing and no shoes. All participants will be scanned at the same time of day at baseline and final day 2 under similar conditions to minimize the impact of fluid effects. DXA operators will be ISCD-certified.

D₃-creatine Dilution Method for Muscle Mass

This technique is a novel method to measure skeletal muscle mass based on creatine and creatinine biology.^{66,67} Participants will ingest a single 60 mg dose of stable D₃-creatine on Day -3 enrollment and again on final day 1. The D₃-creatine is procured from Cambridge Isotope Laboratories (catalog# DLM-1302-MPT). D₃-Creatine is encapsulated by Greenpark Pharmaceuticals (Houston, TX) as a 60 mg dose in each capsule. To measure total body creatine pool size and muscle mass, the second void of fasting morning urine will be collected 3 days following the dose (baseline and final day 2 visits). A urine will also be collected on final day 1 to subtract any remaining D₃-creatinine from the baseline dose. The urine will be measured for D₃-creatinine enrichment in the urine, which will be determined by LC-MS/MS at the University of California at Berkeley. To minimize variability in this muscle mass measurement, participants will be asked not to eat foods containing creatine or creatinine (animal products) after their mid-day meal on the day prior to these urine collections on day 0 (Baseline), day 164 (Final Day 1) and day 168 (Final Day 2). In a subset of participants coming in for a Week 1 safety lab, we will also request a second void of fasting morning urine. The purpose of performing this additional urine sample in our ongoing study is to evaluate if it is necessary to account for the dietary creatine load from the whey. By adding a spot urine 1 week on supplementation, we will calculate the 1-week difference in the D₃-creatine tracer pool size from Baseline. Should we detect a difference, then this difference would be an adjustment factor in our analysis. A handout will be provided to guide participants in what they should and should not eat on these three occasions.

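### The 24-hour urines and the linked baseline recall fall on days when animal products are restricted for the D₃-creatine test, so they cannot be the normal days the protocol requires

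*Protocol*

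**What the plan says.** **Recalls and urine.** Footnote d of the protocol's study procedures chart states: "Three consecutive 24-hr dietary recalls will be done for 3 days at the beginning of the study (between the Enrollment and Baseline visits"). Its dietary assessment section links the last of these to the urine: "The third recall day will coincide with the 24-hr urines collected for NAE, Ni, and Cr". Footnote h lists the collections: "Baseline visit and Final 2 visits: Ni, NAE, Cr". The chart shows them as returned at those two visits, Day 0 and Day 168. One further recall is tied to Final Day 2.

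**Usual-diet rule.** The same dietary section says: "Both the recalls and urine collections will be done on “normal days” so as to be most representative". The stated aim is to capture what the person ordinarily eats.

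**D₃-creatine restriction.** The D₃-creatine section says: "Participants will ingest a single 60 mg dose of stable D₃-creatine on Day -3 enrollment and again on final day 1". It then adds: "participants will be asked not to eat foods containing creatine or creatinine (animal products) after their mid-day meal on the day prior". The collections meant are the fasting urines of Days 0, 164 and 168.

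**Packets.** Footnote j has the evening packet skipped on Days 164 and 168 themselves.

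**Use of the data.** UNi is a secondary outcome. The protocol (Objectives and Endpoints) specifies it adjusted for nitrogen intake. SAP section 7a lists it without that adjustment, and section 7b analyses it by an approach similar to the primary ANCOVA. SAP section 5b names UNi and NAE as the objective adherence measures. SAP section 7c forms subgroups at 0.8 g/kg/d on the three-day recall mean and at 15 mmol/day for NAE.

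**The concern.** Two instructions collide. One wants the urine and recall to show the participant's ordinary diet. The other changes that diet for the afternoon and evening of the same day. Nothing in either document reconciles them.

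The chart has only two 24-hour urines, at Baseline and Final Day 2. The final one is therefore the only on-treatment measurement of UNi and NAE, and it describes a day on which intake was altered by instruction. At baseline, the altered day is one of the three in the protein mean that defines a SAP subgroup. Because entry requires habitual intake of no more than 0.8 g/kg/d, participants whose recalls exceed 0.8 plausibly lie close to the cut, where a small downward shift changes their class.

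**Working it through.** The plan states no figure for this point, so there is none to reproduce. The check aligns the schedule and then sizes the effect under stated assumptions.

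**1. Calendar**
- Enrollment is Day -3 and Baseline is Day 0. Three consecutive intake days between them are Days -3, -2 and -1, so the third is Day -1.
- The baseline urine coincides with that day and is returned on Day 0, so it runs from Day -1 to Day 0.
- The final urine is returned on Day 168, so it runs from Day 167 to Day 168.
- The restriction falls on the day before Days 0, 164 and 168, that is on Days -1, 163 and 167, after the mid-day meal.
- Days -1 and 167 therefore carry both the urine and the restriction. Day 163 has no 24-hour urine.

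**2. Size of the shift in recorded protein**

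The documents do not give evening intake. Assumptions: 30-50% of daily protein is eaten after mid-day, 50-80% of that is animal protein, and 0-50% of it is replaced by plant protein.
- Drop on the third day: f = (share after mid-day) × (animal share) × (1 − replacement).
- Low: 0.30 × 0.50 × 0.50 = 0.075. High: 0.50 × 0.80 × 1 = 0.40.
- Drop in the three-day mean: f/3 = 0.025 to 0.133.
- A true 0.80 g/kg/d then reads 0.80 × (1 − 0.025) = 0.78 down to 0.80 × (1 − 0.133) = 0.69.
- Habitual intake that reads as exactly 0.8: 0.8/(1 − f/3) = 0.82 to 0.92 g/kg/d.

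**3. Nitrogen intake on the urine day**

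Assumptions: 6.25 g protein per g nitrogen, body weight 60-80 kg, intake 0.8 g/kg/d.
- Usual intake: 48/6.25 = 7.7 g to 64/6.25 = 10.2 g N/d.
- Reduction: 0.075 × 7.68 = 0.6 g to 0.40 × 10.24 = 4.1 g N.
- This is the fall in intake. Excretion within the collection need not follow one evening's intake in full.

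**4. Packet skip, conditional only**
- If the packet were skipped on the evening of Day 167, one of three daily packets would be lost during the final urine: 15-25 g protein, or 15/6.25 = 2.4 g to 25/6.25 = 4.0 g N. The supplement supplies 7.2-12.0 g N/d.
- That nitrogen loss would occur in the whey arms only, because the placebo powder is maltodextrin.
- Footnote j places the skip on the evening of Day 168, after that urine has been returned. Taken literally, nothing is lost.

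**The case against.** The strongest reply is that this concerns one evening and leaves the comparison intact. Several parts of that reply stand.

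- **No bias by itself in the randomized contrast.** A reader might infer that the estimated effects on UNi are distorted. The documents do not support this. The diet restriction applies to all arms at both visits, and the secondary models adjust for the baseline value.
- **The arm-specific loss is not in the plan as written.** A reader might infer that the whey arms lose a packet during the collection. Footnote j does not say so. The possibility arises only because its timing does not match the evening-before restriction in the D₃-creatine section.
- **Subgroup reclassification is easily overstated.** Suppose 20-30 g of protein is removed, with no replacement, at 70 kg. The mean then falls by 20/3/70 = 0.095 to 30/3/70 = 0.143 g/kg/d, and a true 0.9 reads 0.805 to 0.757. At 20 g the participant stays above 0.8; at least 0.1 × 3 × 70 = 21 g must go. Since 0.9 g/kg at 70 kg is 63 g/d, 20-30 g is 32-48% of the day's protein, and plant protein is not barred.
- **The adherence markers probably still work.** The supplement adds 7.2-12.0 g N/d in the whey arms only, against a dietary shift common to all arms. The protocol puts the potential renal acid load of the whole whey quantity at about +15, against 81 mmol/d of KHCO₃.
- **Eligibility is separate.** It rests on the prescreening questionnaire and an in-person dietary assessment at screening.

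One further caution: no section names the calendar day of the urine. It is inferred from the recall window and the return visit. If practice already avoided the overlap, a clarifying sentence would settle the matter. None of this reconciles the two written instructions, and the protocol's safeguard for UNi, adjustment for nitrogen intake, is missing from the SAP.

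**Conclusion.** The scheduling conflict holds. As written, the baseline urine with its linked recall falls on Day -1 and the final urine covers Day 167, both restricted days. The normal-days rule cannot be met.

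The consequence is a shift in level common to arms and visits: lower UNi, possibly altered NAE, and a lower three-day protein mean. It is not, on its own, a bias in a treatment effect, and leg power is unaffected. Under the assumed evening intakes, the third day reads about 7.5-40% low and the mean about 2.5-13% low. The subgroup cut labelled 0.8 then acts as a cut somewhere between about 0.82 and 0.92 g/kg/d. These figures rest wholly on the assumed shares; only the calendar overlap and the direction for protein intake come from the documents. If the NAE subgroup uses the baseline value, which SAP section 7c does not state, it draws on the same urine.

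The point is worth correcting because the remedy is cheap, not because a main conclusion depends on it.

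**What to change.** **If collections are still to come.** Finish the 24-hour urine and its linked recall before the restriction begins, for example from Day -2 to the morning of Day -1 and from Day 166 to the morning of Day 167. This means changing the participant instructions and naming the second baseline recall, not the third, as the linked one. It needs no extra visit or assay; the completed urine is held about a day longer before return. It does not repair the three-day mean, which still contains Day -1. Three unrestricted consecutive days would have to start on Day -4, before the Enrollment visit and its consent.

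**For data already collected.** The SAP describes the trial as conducted, with final analysis still to follow, so this may be the main route.
- Flag the UNi and NAE values that come from restricted days.
- Add to the SAP the nitrogen-intake adjustment of UNi that the protocol specifies. Since whey itself raises nitrogen intake, state whether packet nitrogen counts, and show the unadjusted result beside it.
- Repeat the protein subgroup analysis with the mean of Days -3 and -2. The cost is a slightly noisier two-day mean.

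**Separately.** Footnote j (packet skipped on the evenings of Days 164 and 168) and the D₃-creatine section (restriction on the evening before) must be reconciled. Record when each participant actually skipped the packet, because a skip on Day 167 would affect UNi in the whey arms only.
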